- 4. Develop, implement and assess strategies to recruit, train, and integrate peer CHW health coaches within the PCMH model.

The 36-month intervention will be conducted using a staggered entry design across four, overlapping, 12-month waves to account for CHW caseload limits. This study will test a scalable model of peer health coaching to address the millions of patients at risk for DM, using low cost, culturally congruent personnel to promote prevention of DM in PCMH practice. If successful, our study team will work with VA's Central Office and NY City's Health and Hospital Corporation to translate the model for larger scale implementation.

Characteristics of the Research Population

Number of Subjects

All 12 PC teams at VA NY Harbor and all 4 PCMH teams at BH will be eligible to participate. In our VA PROVE study, 51/52 PCPs participated in the intervention, and we expect similar rates in this project. Eligible patients will be identified through the study's pre-DM registry, which will be based on the EMR and Corporate Data Warehouse (CDW) at each site. This methodology builds on our ongoing national, retrospective cohort study of predictors of DM among veterans with pre-DM back to 2008. Based on preliminary analysis of VA NYHHS data from 2010-2012, 62% of veterans enrolled in PC without DM, have had an HbA1c test in the previous two years.

In the intervention group, we anticipate contacting 2,100 randomly selected patients (1,050 at the VA* and 1,050 at BH) to ultimately enroll about 1,100 patients (550 at the VA and 550 at BH). This outreach sample reflects our assumption that 20% of patients will be unreachable and that 60% of those reached will enroll in the study. Another 1,100 patients attributed to control group providers will be randomly selected as the control group, in accordance with the waiver of HIPAA authorization. As detailed below, the control group will not participate in the CHW intervention. The total sample, including the intervention and control groups, will be about 2,200 patients. This amounts to approximately 265 patients (across intervention and control groups) per wave and per clinical site.

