Survey of providers: We will conduct a survey of primary care providers to assess the impact of the intervention on staff with measures described below to understand implementation issues. The survey will be conducted at baseline and following the 3-year intervention, using a mixed approach, including hard copies, in person or in office mailboxes, and email. In our previous study, we had a 65% response rate from providers and nurses, and we anticipate a similar response rate in the proposed study. A statement will be included with the survey outlining the number of times the survey will be conducted (2) and the timeframe for the surveys.

Semi-structured interviews: To further understand the clinic staff's lived experience of the CHW intervention, we will conduct brief, semi-structured interviews of the providers at baseline and semi-annually, for a total of 6 times (baseline, and after years 1, 1.5, 2, 2.5, and 3) with a subset of participating PCPs identified as key informants based on their experience and institutional knowledge. To understand any changes in how teams collectively integrate CHWs into their practices, we will also conduct brief, semi-structured interviews with primary care team members other than providers at the same intervals. Through these surveys and interviews, we will assess key aspects of the implementation of the CHW intervention as experienced and perceived by clinic staff. To additionally understand factors that impede or facilitate the implementation of the intervention, we will conduct semi-structured interviews annually (after years 1, 2, and 3) with practice administrators at each health care organization; key informants knowledgeable about population health and health policy at city level as relevant to DM prevention; and staff at the nutrition and exercise programs, whose involvement in the program can enable implementation success. Interviews will continue until emerging themes are saturated, anticipating up to 25 subjects at each site (approximately 20 involved in primary care delivery, 2 in managerial or administrative roles, and up to 3 staff at nutrition and exercise programs) and up to 5 informants outside the two sites who can speak to macro-level factors. These interviews will be audio-recorded and transcribed for analysis.

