Staff survey data will be used to assess the self-efficacy and collective-efficacy as a team in preventing DM and in working with a CHW coach. We will compare baseline and post-intervention scores on each of the measures. To test the hypothesis that staff assigned to the intervention teams who work closely with a CHW will improve their self and collective efficacy of DM prevention and CHW coaching, we will compare post-intervention scores for these measures across the study arms using linear regression and controlling for baseline scores and adjusting for staff roles, length of time in their role and site. Survey data will also be used to assess PCPs' readiness to work with CHWs for DM prevention. Baseline and post-intervention scores will be compared using Wilcoxon signed-rank tests.

All interviews transcripts (from PCMH and other staff, practice administrators, CHWs, and key informants) and observations of study team meetings and case conferences will be analyzed for common themes by two independent researchers for qualitative analysis. First, two researchers will read the transcripts to identify key domains. Second, the researchers will independently code two of each set of transcripts. They will then meet to develop initial codebooks with code names and meanings. Third, each coder will apply the codebook to the remaining transcripts. Fourth, coders will meet to compare codes and identify patterns and common themes throughout the transcripts. Baseline interviews will be used to guide toolkit refinement and to explore anticipated facilitators and barriers to incorporating CHWs into the PCMH workflow. Mid- and post-intervention interview data will help us to determine key barriers, facilitators and lessons learned from staff, CHWs, and key informants regarding the implementation of CHWs in PC practice.

To assess implementation fidelity, baseline and 6-monthly scores on the coverage, duration, and frequency of CHW-patient contact for BH and VA patients will be compared using ANCOVA. Content of delivery will also be assessed qualitatively based on a sample of CHW-patient contacts. Implementation fidelity will be compared across BH and the VA to examine if differences in organizational setting shape the implementation process.

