All primary care staff will be given information about the proposed research during regular staff meetings, email announcements and a study flyer and then asked to participate. Staff providing verbal consent to participate will be randomized (as part of their PACT team) to either work with a CHW or serve as controls. Staff who opt-out will not be randomized, although might still work on a team that is included in the study. For example, if one primary care provider in a team declines participation, the other providers and team members consent, the team will be randomized to a study arm. If that team is randomized to an intervention arm, the

CHW would only work with the patients of the consenting providers. We anticipate that we will be able to obtain sufficient numbers of staff consenting to participate, as in our previous panel management study only one PCP out of fifty-one declined, and a majority of staff reported that the interventions and CHW support were helpful. Lastly, as CHWs will be extending services and interventions that are a part of regular, evidence-based practice on behalf of patients' primary care physician, patients will not individually consent to receiving phone calls, mailings, or any other contact with the CHW. For surveys, which are research procedures specific to this study, consenting elements will be presented at the top of the survey. Primary care teams will pre-approve all lists of patients receiving interventions as well as approving the content of the CHW's intervention. Patients will have the right to opt out of receiving outreach at any time. All mail materials will include instructions on how to stop receiving mail from the CHW.

A waiver of authorization for both recruitment/identification purposes and for study procedures has been sought. We use the electronic medical record to generate a list of eligible participants, in order to approach them to screen for eligibility. Without the requested Waiver, screening could not be practically carried out and would adversely affect the scientific rigor of the study.

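### PCP readiness to work with CHWs is analysed only before versus after, with no comparison between the randomised arms, so a shared 3-year change could be mistaken for an intervention effect

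*Combined protocol and SAP*

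**What the plan says.** The section Analysis: Intervention Implementation treats two groups of staff-survey measures differently.

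- **Self- and collective efficacy.** Baseline and post-intervention scores are compared. To test a stated hypothesis about intervention-team staff, the plan then adds: "we will compare post-intervention scores for these measures across the study arms using linear regression and controlling for baseline scores". That model also adjusts for staff role, time in role and site.
- **PCP readiness.** This is introduced afterwards: "Survey data will also be used to assess PCPs' readiness to work with CHWs for DM prevention". The only analysis given is "Baseline and post-intervention scores will be compared using Wilcoxon signed-rank tests".

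Under Implementation Research, the provider-survey paragraph states the purpose ("We will conduct a survey of primary care providers to assess the impact of the intervention on staff") and the timing ("The survey will be conducted at baseline and following the 3-year intervention"). The section on subject identification, recruitment and consent says that consenting staff "will be randomized (as part of their PACT team) to either work with a CHW or serve as controls".

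**The concern.** A signed-rank test on paired scores asks whether readiness moved between the two surveys. It does not ask whether it moved more in teams given a CHW. Over 3 years readiness could shift in both arms for reasons unrelated to the programme, and the planned test cannot tell such a shift from an effect.

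This matters because the survey is introduced as a measure of the intervention's impact on staff, and because a significance test, not only a summary, is specified for readiness. A small p-value could then be reported as impact although the randomised comparison had not been made. The reverse error is also possible: if both arms are pooled in the test, a real effect is diluted by the controls.

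**Working it through.** The documents give no sample size, power or effect size for readiness, so there is no planned figure to reproduce.

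**1. Does any stated between-arm analysis cover readiness?** The regression sentence refers back to measures already named, which are self- and collective efficacy. Readiness is introduced only afterwards and given a different method. No other section compares readiness by arm.

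**2. What each analysis estimates.** Let *s* be the change common to both arms and *e* the intervention effect.

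- Signed-rank, intervention PCPs only: responds to *s* + *e*.
- Signed-rank, both arms pooled, equal split: average change is *s* + *e*/2.
- Between-arm, baseline-adjusted: responds to *e*; *s* cancels.

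With *e* = 0, both signed-rank versions still respond to *s*. The plan does not say whether the test is pooled, run within each arm, or restricted to the intervention arm. None of these is a between-arm contrast.

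**3. Are control data available?** The provider survey is not restricted to intervention teams, and the efficacy regression needs baseline and follow-up scores from both arms. Control-arm surveys at both times are therefore implied. It is not stated outright that control PCPs answer the readiness items.

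**4. Illustration of size.** From the documents: the survey paragraph says of the team's previous study that "we had a 65% response rate from providers and nurses", and a similar rate is expected. If that rate applied to PCPs in each round, paired completers would be between 0.65 × 0.65 = 0.42 (independent response) and 0.65 (same people both times).

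Assumed, not in the documents: 50, 80 or 100 PCPs split equally; normal scores; baseline to follow-up correlation 0.5; no clustering; *e* = 0. At correlation 0.5 the SD of the paired difference is √(2 × (1 − 0.5)) = 1, so shifts are the same in score-SD and difference-SD units. These assumptions give 21 to 65 pairs overall and 10 to 32 in the intervention arm. Each scenario used 3,000 simulated trials and a two-sided 0.05 level. The table shows the percentage of trials with a significant result, as the range over the six combinations of PCP number and response.

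| Shared shift | Signed-rank, all PCPs | Signed-rank, intervention only | Between-arm regression |
|---|---|---|---|
| 0 | 4.4 to 5.6 | 3.9 to 4.9 | 4.3 to 5.3 |
| 0.3 SD | 24 to 65 | 12 to 37 | 4.5 to 5.5 |
| 0.5 SD | 56 to 97 | 29 to 76 | 4.4 to 5.3 |

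**5. Clustering.** The recruitment section randomises staff by team, and Number of Subjects says "All 12 PC teams at VA NY Harbor and all 4 PCMH teams at BH will be eligible to participate", so there are at most 12 + 4 = 16 teams. The efficacy regression as written states no team effect. The simulation has none either, so its rate of about 5% for the between-arm model is not shown to hold for clustered data. With intercept, arm and site fitted at team level, at most 16 − 3 = 13 degrees of freedom remain for the arm comparison.

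**The case against.** **Readiness may be meant as description.** No hypothesis is attached to it, the section concerns implementation, and the survey also serves to understand implementation issues. This stands in part: reading a change as an effect is an inference from the survey's stated purpose, not a claim the plan makes for readiness. If description is intended, the plan should say so.

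**Readiness to work with CHWs is hypothetical for controls, who have no CHW access.** That is true of their follow-up scores. But the efficacy measures include working with a CHW coach and are still compared across arms, and every PCP answers from the same position at baseline. This limits interpretation without removing the value of the comparison.

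A reader might also infer stronger points that the documents do not support:

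- *That only readiness gets a before-after comparison.* Efficacy gets one too; the difference is its additional between-arm regression.
- *That control readiness data are collected and thrown away.* Their collection is implied, not stated, and a test run within each arm would use them.
- *That restriction to providers answering both surveys counts against the signed-rank test.* A baseline-adjusted regression needs both scores too unless they are imputed, so the 42% to 65% range applies equally to the remedy.
- *That ignoring teams sets the signed-rank test apart.* The efficacy model states no team effect either.
- *That a drift of a particular size should be expected.* The documents give none.

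**Conclusion.** The point holds as an omission: readiness has no stated between-arm analysis, and a before-after test cannot separate the programme from a change common to both arms. That follows from the form of the test and needs no assumption about numbers.

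The size is conditional. The 12% to 97% range rests on assumed PCP numbers, a correlation of 0.5 and shared shifts of 0.3 to 0.5 SD, none of which the documents supply. The 65% response rate comes from providers and nurses in an earlier study, not from PCPs in this trial. The figures show that a misleading result is possible, not that one is likely.

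The consequence is small. Readiness is an implementation measure with no stated decision resting on it, and the analyses of diabetes incidence, weight and patient activation are unaffected.

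**What to change.** Add to Analysis: Intervention Implementation that post-intervention readiness will be compared between the randomised arms, adjusted for baseline readiness and the covariates already listed for efficacy, using an ordinal model or rank-transformed scores. Allow for team clustering with a small-sample method suited to at most 16 teams, such as a team random effect with corrected degrees of freedom, and make the same addition to the efficacy regression.

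Keep the signed-rank test as a within-arm description, reported for each arm. Confirm that control PCPs complete the readiness items at both surveys. State how a missing baseline or follow-up score will be handled, since the new model needs both unless scores are imputed.

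The cost is a short amendment. If control PCPs already answer these items, as the efficacy regression implies, no new data, visits or participants are needed. If readiness is meant only as description, the minimum change is to say so and to state that the before-after result will not be presented as an intervention effect.

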CHW Recruitment: We will hire and train 6 CHWs (3@VA, 3@BH), from local patient support organizations (Veteran Service Organizations and BH volunteer office, as we have done in prior CHW studies) to implement the toolkit strategies. CHW employment opportunities announcements will be created. Requirements will include: 1) evidence of a leadership role in the patient community through social support or advocacy organizations; 2) strong communication and interpersonal skills; and 3) a high school education or GED. CHW candidates will not be required to have a background in health. Personal experience with DM will not be required.

CHW Training: We will train the CHWs in key DM concepts, motivational interviewing, brief action planning, and stages of behavior change. CHWs will participate in a 105-hour core competency training developed collaboratively developed by [name] and her team and the Community Health Worker Network of New York. CHWs will conduct mock telephone counseling calls with trained standardized patients to enhance skills, gain feedback, and develop confidence in these techniques. In addition to these training experiences, CHWs will have letter templates, motivational interviewing scripts, and protocols available for patient outreach to standardize and guide patient outreach

CHW Intervention

At each wave's outset, ~ 250 patients at each study site will be randomly selected for outreach and paired with one of five CHWs (2 at BH, 2 at VA, 1 at both clinics). Researchers will provide each intervention group PC provider their selected list of prediabetic patients. PCPs will be asked to review the list to identify anyone they think should be excluded from the intervention. Patients are matched to a CHW according to the patient's language and neighborhood of residence, as the study aims to cluster CHWs' patients to facilitate CHW travel and expertise in local resources. We mail selected patients a letter on behalf of their PCP alerting them of their DM risk status, available prevention resources, and introducing them to their assigned CHW. CHWs will then call patients to describe the program and seek verbal informed consent to enroll in the study. Patients who decline participation will be asked if they are willing to be invited again in subsequent waves of the study. CHWs will continue outreach until they have met their caseload for the wave.

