Process indicators: In this pragmatic trial, we will systematically track and examine the process of implementation and the contextual factors that influence implementation of the CHW intervention. To do so, we will draw on available study data in REDCap, the secure program used to record CHW-patient encounters for the study. At the end of the study we expect to have data on approximately 1,000 enrolled intervention patients, with each patient followed for one year, with CHW-patient contacts limited to the intensity that patients are willing to attend. From REDCap, we will collect data semi-annually on four indicators of implementation fidelity, namely (1) the content of CHW activities, (2) the coverage (number of patients reached), (3) duration (how long each patient is followed up), and (4) frequency (how often patients are contacted) of CHW-patient contacts. Content of CHW activities will be assessed through assessing CHW case notes on a random selection of 15 enrolled patients and interviews with CHWs. Case notes will be assessed to examine how CHWs handle patients' behavioral barriers and social needs, including the referrals they make to various services (e.g., mental health, social work, exercise programs). To understand barriers that CHWs confront in the course of implementation, we will conduct semi-structured interviews with the CHWs and identify major themes (questions, concerns) related to behavioral counseling and referrals that may be discussed during the study team's meetings and case conferences. Similar to the semi-structured interviews with providers and other primary care team members, interviews will be conducted at end of year 1, 1.5, 2, 2.5, and 3. Findings resulting from analysis of patient case notes and other CHW materials will be reported anonymously.

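### The BH–VA comparison of implementation fidelity ignores clustering of patients within five or six CHWs, and its coverage measure does not suit the planned ANCOVA

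*Combined protocol and SAP*

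**What the plan says.** The section Analysis: Intervention Implementation plans an ANCOVA of "baseline and 6-monthly scores on the coverage, duration, and frequency of CHW-patient contact", comparing BH with VA patients. The purpose follows: "Implementation fidelity will be compared across BH and the VA to examine if differences in organizational setting shape the implementation process".

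The indicators are defined under Process indicators: "the coverage (number of patients reached), (3) duration (how long each patient is followed up), and (4) frequency", the last being how often patients are contacted. The source is also given there: "From REDCap, we will collect data semi-annually on four indicators of implementation fidelity".

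Four other places bear on how these indicators behave:

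- **CHW Intervention.** Contact starts after selection and a letter: "CHWs will then call patients to describe the program and seek verbal informed consent to enroll in the study". On when it stops, "CHWs will continue outreach until they have met their caseload for the wave". This section pairs patients with one of five CHWs: two at BH, two at VA and one at both.
- **CHW Recruitment.** The number to be hired is six, three per site.
- **Statistical Power and Sample Size.** Fidelity calculations, coverage included, rest on all enrolled patients, and power is said not to apply.
- **Process Evaluation.** The CHW Coordinator assesses each quarter the proportion of patients reached and engaged, by site and by CHW.

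**The concern.** Frequency and duration of contact are things the CHW does. Patients of one CHW will tend to resemble each other on both, because they share that CHW's habits, availability and skill. The mixed models for clinical outcomes allow for correlation within providers and teams, but the fidelity ANCOVA names no CHW term. With two or three CHWs per site, site is almost entirely confounded with a few individuals. An analysis that treats about a thousand patients as independent will give intervals that are too narrow, and the plan intends to read the result as an effect of organisational setting.

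Coverage has a different problem. A count of patients reached has no patient-level value to put into an ANCOVA. Restricting it to enrolled patients removes all variation. The raw count is also hard to read as fidelity: a site with a lower consent rate must reach more people to fill the same caseload, and would show higher coverage.

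Finally, an ANCOVA adjusts for a baseline score, and the plan does not say what baseline means for a contact that exists only because of the study.

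**Working it through.** **The plan's own figures.** Statistical Power and Sample Size gives 72 patients per full-time CHW per wave, 3.5 full-time equivalents and 4 waves: 72 × 3.5 × 4 = 1,008 enrolled. With 20% unreachable and 60% of those reached enrolling, the number to select is 1,008 / (0.80 × 0.60) = 2,100. Both agree with the text. The number reached is 2,100 × 0.80 = 1,680.

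**Clustering by CHW.** The documents give no CHW-level ICC, so 0.02–0.05 is assumed. Equal CHW loads and an even site split, 504 patients each, are also assumed. The true error of a nominal 5% test is 2 × P(Z > 1.96 / √DE), where DE is the design effect.

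*Six CHWs, three per site.* Patients per CHW: 1,008 / 6 = 168. DE = 1 + 167 × ICC.

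*Five CHWs, one split evenly between sites.* Patients per CHW: 1,008 / 5 = 201.6. Each single-site CHW carries weight 201.6 / 504 = 0.4 in the site mean; the shared CHW has 0.2 at each site and cancels from the difference. In units of the total variance, the variance of the site difference is 4 × 0.4² × ICC + 2 × (1 − ICC) / 504. Dividing by the independent-patient value 2 / 504 gives DE = 1 + 160.28 × ICC.

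| ICC (assumed) | Six CHWs: DE | Error | Five CHWs, one shared: DE | Error |
|---|---|---|---|---|
| 0.01 | 2.67 | 23% | 2.60 | 22% |
| 0.02 | 4.34 | 35% | 4.21 | 34% |
| 0.05 | 9.35 | 52% | 9.01 | 51% |

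The row at 0.01 lies below the assumed range and shows that the error is still more than four times nominal there.

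**Coverage.** As a count it yields 2 sites × 4 waves = 8 values, or 2 sites × (36 / 6) half-years = 12 values. On enrolled patients only, every patient has been reached, because enrolment requires a completed CHW call; coverage is 100% at both sites with zero variance. As a raw count it moves with consent. Filling 504 places at one site takes 504 / 0.50 = 1,008, 504 / 0.60 = 840 or 504 / 0.70 = 720 patients reached at consent of 50%, 60% or 70% (the 50% and 70% are assumed). The site with the worst consent shows the highest count.

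**Baseline.** If baseline means before CHW contact, the score is zero for every patient. An ANCOVA on 504 patients per site with illustrative Poisson contact counts and an all-zero covariate had a design matrix of rank 2 out of 3. The site estimate (1.083), standard error (0.199) and residual degrees of freedom (1,006) equalled those of the plain two-group comparison. The covariate drops out and the contrast remains estimable.

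**The case against.** The strongest reply is that this is a process comparison with no stated alpha, threshold or decision rule. It sits beside a qualitative assessment of content, and no patient outcome depends on it. That is correct and limits the weight of the point. It does not remove it, because the plan states the inference it wants to draw about organisational setting.

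The size of the clustering effect rests on an assumed ICC and on equal loads, and 3.5 full-time equivalents spread over five or six people makes equal loads doubtful. This stands as a caution on the exact figures.

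The Process Evaluation section already tracks the proportion reached by site and CHW, so a usable coverage measure exists. That stands too, but the planned fidelity analysis does not use it.

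Three stronger readings are tempting, and the documents do not support them:

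- A reader might infer that caseload fixes coverage. Caseload limits enrolment, not the number reached: 1,680 against 1,008 on the plan's own rates. Even 1,008 is called a minimum, and Number of Subjects expects about 1,100.
- A reader might infer that the baseline scores are zero by design. The plan does not define them, and the first semi-annual reporting period is possible. That value would itself measure early delivery, so adjusting for it could remove part of the site difference sought.
- A reader might infer that the site comparison cannot be done at all. For frequency and duration it can: contact intensity varies by patient, and a constant covariate does no harm.

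**Conclusion.** The point holds in two main respects. Without a CHW term, the standard errors for the BH–VA difference in frequency and duration are too small: the design effect is about 4.2–9.4 and the true error of a nominal 5% test about 34–52%. These figures assume an ICC of 0.02–0.05, equal loads, an even site split and no CHW turnover; turnover would add clusters and lower the design effect. They cover both CHW numbers in the protocol. Coverage, as defined, does not suit a patient-level ANCOVA, is constant if restricted to enrolled patients, and is distorted by consent rates as a raw count.

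The undefined baseline is a lesser matter of specification. The whole point is minor for the trial: it concerns a secondary implementation analysis and leaves the primary outcome untouched.

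**What to change.** Amend Analysis: Intervention Implementation as follows.

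1. Define coverage as patients reached divided by patients selected for outreach, by site and wave, in line with Process Evaluation. Remove coverage from the calculations based on enrolled patients. Because outreach ends when caseloads are full, also report how many selected patients were actually called, so that those never tried are not counted as unreachable.
2. Model contacts per patient-month and duration over the 6-monthly periods with site as a fixed effect and CHW as a random effect, using a count or linear model as suits the outcome.
3. Drop the baseline term if it means before CHW contact. If it means the first reporting period, say so and justify adjusting for it.
4. Report the site difference with its interval as descriptive. Six CHWs in two sites leave only 6 − 2 = 4 degrees of freedom between CHWs, so the variance between them will be poorly estimated.
5. Reconcile the five and six CHWs given under CHW Intervention and CHW Recruitment.

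The REDCap records and outreach lists suffice, so only the analysis wording changes. The cost is wider intervals and a weaker claim about organisational setting.
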